2.1.2 Prior or concomitant medications (other than anticancer therapies)

All medications taken by the patient within 21 days prior to first study treatment, at any time during the study in addition to IMP will be reported in the eCRF.

The following information will be collected in the medication eCRF page: drug/medication (brand or generic name), reason (eg, curative, prophylaxis, etc), dose and unit, route, start date and end date (if applicable)/ongoing (otherwise).

All medications will be coded using the World Health Organization-drug Dictionary (WHO-DD) version in effect at Sanofi at the time of database lock.

- Prior medications are those the patient used prior (<) to first study treatment administration. Prior medications can be those discontinued before first administration or those ongoing during the treatment phase.
- Concomitant medications are any treatments received by the patient concomitantly to study treatment, from first dose to the date of last administration + 30 days. A given medication can be classified both as a prior medication and as a concomitant medication. Any anti-cancer treatment administered after the date of the last study treatment administration will not be considered as a concomitant medication and will be regarded as further anti-myeloma therapy regardless of the date of initiation (see [Section 2.4.10](#)). The analysis of concomitant medications will include premedication (see below).
- Post-treatment medications (excluding post anticancer treatments) are those the patient took from 31 days after last study treatment administration up to the end of the study.

IR medications

As defined in Section 8.2 of the study protocol, patients were to routinely receive premedications prior to isatuximab infusion to reduce the risk and severity of hypersensitivity reactions commonly associated with monoclonal antibodies. Premedications are defined in the protocol as non-investigational medicinal product(s). Premedications are reported on a specific eCRF page.

Analysis of premedications will focus on those given for prophylaxis reason. Medication given in curative intent of IR will be also analyzed.

Any technical details related to computation, dates, and imputation for missing dates, are described in [Section 2.5](#).

2.1.3 Efficacy endpoints

Response assessments were to be performed on Day 1 of every cycle during treatment by investigators using the International Myeloma Working Group (IMWG) response criteria (1) and by considering the assessment included in Section 1.4.

Biological responses (\geq PR) and progression should be confirmed on 2 consecutive biological (serum and/or urine M protein) disease assessments. No confirmation is required for radiological assessment.

For Phase 1, best overall response, duration of response, progression free survival and overall survival will be derived and listed by patient.

2.1.3.1 Primary efficacy endpoint (Phase 2 only)

The primary efficacy endpoint is ORR, defined as the proportion of patients with CR (including sCR), VGPR or PR as BOR as assessed by the investigator. BOR will be derived using disease assessments (overall response CRF page) from the start of treatment through the entire study excluding any assessments performed after disease progression (that is confirmed), the cutoff date or following the start of further therapies for MM (see Figure 1). The ordering of evaluations from best to worse is: sCR, CR, VGPR, PR, MR, stable disease (SD), progressive disease (PD), not evaluable (NE). BOR for patients without response assessment will be 'Not evaluable'. BOR will be the best sequential response based on the investigator's disease assessments as determined by the criteria in Table 3. In addition, the following rules will be applied:

- BOR will be NE for patients who received at most 2 isatuximab administrations with investigator assessment of response of SD or better at Cycle 1 or end of treatment.
- BOR will be PD for patients without response assessment who received 1 cycle of treatment and died due to PD or had symptomatic deterioration within 30 days of last study treatment administration.

Symptomatic deterioration will not be considered as progression in the primary analysis of ORR.

Table 3 - Sequential response determination for investigator response assessment

Overall response at Cycle n	Overall response at Cycle n+1 ^a	Sequential response
sCR	sCR	sCR
CR	sCR	CR
sCR	CR	CR
CR	CR	CR
sCR/CR	VGPR	VGPR ^b
sCR/CR	PR	PR
VGPR	sCR/CR/VGPR	VGPR ^b
VGPR	PR	PR

Overall response at Cycle n	Overall response at Cycle n+1 ^a	Sequential response
PR	sCR/CR/VGPR/CR/PR	PR
sCR/CR/VGPR/PR	NE/No further evaluation/SD/PD	MR ^c
MR	Any	MR
Any	MR	MR
NE/SD/PD	sCR/CR/VGPR/PR	MR ^c
NE/PD/SD	SD	SD
SD	No further evaluation/NE/PD	SD
NE	SD	SD
PD	No further evaluation/NE	unPD ^e
PD	PD	PD
NE	PD	unPD ^e
NE	No further evaluation	NE
No evaluation ^d		PD ^d

a Disease assessment are planned to be performed every cycle. Disease assessment performed after the start of new anticancer treatment will be excluded from the derivation of BOR.

b Sequence provided for programming purpose.

[figure not shown]
c Unconfirmed PR or CR will be considered MR.

d Only for analysis based on investigator assessment, BOR will be PD for patients without response assessment who received 1 cycle of treatment and died due to PD or had symptomatic deterioration within 30 days of last study treatment administration.

e Unconfirmed PD, unless PD is based on radiological assessment that does not need confirmation.

BOR=best overall response; sCR=stringent complete response; CR=complete response; MR=minor response; NE=not evaluable; PD=progressive disease; PR=partial response; SD=stable disease; VGPR=very good partial response.

Figure 1 - Determination of BOR when disease assessments are performed after new anti-myeloma therapies are started or performed after the cutoff date

DA= Disease assessment – PR=Partial response; PD= progressive disease.

① DA3 and subsequent are excluded from the BOR determination. BOR will be MR.

② DA2 will be used to confirm PD since PD was first documented at DA1 before initiation of a new anti-myeloma therapy. BOR will be PD.

③ DA5 and subsequent will be excluded from the analysis since performed after the cutoff date. BOR will be MR.

Subgroup analyses of BOR will be performed for the variables listed in [Table 4](#).

Table 4 - List of variables for subgroup analyses

Variable	Description
Age	<70 years vs ≥70 years
Gender	Male vs female
Number of previous lines of therapy	≤3 vs >3
ISS staging at study entry	I vs II vs III
High risk cytogenetic	Yes vs No
Baseline creatinine clearance (MDRD)	<60 ml/min/1.73m ² vs ≥60 ml/min/1.73m ²
Refractory to IMiD	Yes vs No
Refractory to PI	Yes vs No
Refractory to IMiD and PI	Yes vs No
Refractory to daratumumab	Yes vs No
Baseline PD-L1 level	≥50% vs <50%

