6.5 DOSE DELAYS/ MODIFICATIONS

6.5.1 General rules

Dose modifications are permitted according to the guidelines described in this section.

Dose modifications different from those stated in the protocol should only be made in consultation with the Sponsor unless required for immediate patient safety.

Dose adjustment and/or cycle delay are permitted in case of toxicity. Dose adjustments will be made according to the worst grade of toxicity observed within a cycle. If a patient experiences several toxicities and there are conflicting recommendations, the most conservative dose adjustment recommended should be followed. Once a dose has been decreased, intra-patient re-escalation back to the previous dose level is not permitted.

Administration of the study treatment will be discontinued in the event of a TEAE that persists despite appropriate dose modifications or any other AE that, in the opinion of the Investigator, warrants discontinuation.

If one of the 2 drugs (cemiplimab or isatuximab) is prematurely permanently discontinued, the other drug can be continued until disease progression, unacceptable adverse reaction, patient's refusal of further treatment, or in the absence of a clear benefit from therapy. The end of treatment assessment in this case will be 30 days after the date of the last IMP administration.

All changes to study treatment administration must be recorded in the eCRF.

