9.2 EFFICACY

9.2.1 Primary endpoint (Phase 2 only)

The second co-primary endpoint of the study is to determine the efficacy of the combination as assessed by ORR. ORR is defined as the proportion of patients with CR (including sCR), VGPR and PR as assessed by investigators using the IMWG response criteria (44).

The following disease assessment procedures will be performed at screening (for eligibility) and again at Cycle 1 Day 1 prior to study treatment administration (baseline for response assessment) and then Day 1 of every cycle during treatment up to progression:

- M-protein quantification (serum and urine) (local laboratory).
- FLC quantification (local laboratory).
- Quantitative immunoglobulins (local laboratory).

- In addition, other examinations for disease assessment will be done as clinically indicated (eg, to confirm a response, suspected PD) as below (local laboratory):
 - Bone marrow aspiration,
 - Bone disease assessment,
 - Extramedullary disease (plasmacytoma) assessment (including bone plasmacytoma).

Response/progression will be determined according to IMWG criteria (44) ([Appendix D](#)). Response/progression based on M-protein and FLC will be confirmed based on 2 consecutive assessments.

Progressive disease is defined for patients with measurable disease with one of the following:

- Increase of $\geq 25\%$ in serum M-protein from nadir (the absolute increase must be ≥ 0.5 g/dL) in 2 consecutive assessments; serum M-protein increases ≥ 1 g/dL in 2 consecutive assessments are sufficient to define relapse if starting M-protein t is ≥ 5 g/dL and/or,
- Increase of $\geq 25\%$ in urine M-protein from nadir (the absolute increase must be ≥ 200 mg/24 h) in 2 consecutive assessments and/or,
- Only in subjects without measurable serum and urine M-protein levels: increase of $\geq 25\%$ in the difference between involved and uninvolved FLC levels and absolute increase must be > 10 mg/dL and/or,
- Definite development of new bone lesions or soft tissue extramedullary disease, or increase $\geq 50\%$ from nadir in the sum of perpendicular diameters of existing soft tissue extramedullary disease lesions if > 1 lesion, or $\geq 50\%$ increase in the longest diameter of a previous soft tissue extramedullary disease lesion > 1 cm in short axis.

Clinical deterioration will not be considered progression in the primary analysis of ORR.

Measurable disease is defined by at least one of the following measurement:

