1.5 MODIFICATIONS TO THE STATISTICAL SECTION OF THE PROTOCOL

- Change from first dose date to randomization date.

Secondary efficacy endpoints ([Section 2.1.3.2](#)) including progression free survival (PFS), time to response (TTR) and overall survival (OS) were defined starting from the first treatment date in the protocol, this is updated to the date of randomization in the analysis plan. The associated censoring rules are also updated.

This change is also applied to disease characteristics variables ([Section 2.1.1](#)), including time from diagnosis to randomization, time from last regimen to randomization, time from last transplant to randomization and time from last radiotherapy to randomization.

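### The SAP's not-evaluable rule for patients with at most two isatuximab doses has no exemption for a confirmed response, so read as written it can count a confirmed responder as a non-responder in the primary ORR

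*SAP*

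**What the plan says.** Protocol 9.2.1 gives the endpoint without any exposure condition: "ORR is defined as the proportion of patients with CR (including sCR), VGPR and PR as assessed by investigators". SAP 2.1.3.1 expresses it through best overall response (BOR), as ORR "defined as the proportion of patients with CR (including sCR), VGPR or PR as BOR as assessed by the investigator". BOR is the best sequential response from Table 3. It uses assessments over the whole study, up to confirmed progression, data cutoff or new myeloma therapy. Note c to Table 3 turns an unconfirmed PR or CR into MR.

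The SAP then continues: "In addition, the following rules will be applied". The first of these rules begins: "BOR will be NE for patients who received at most 2 isatuximab administrations with investigator assessment of response of SD or better". In full it has two conditions:

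- Exposure: no more than two isatuximab doses.
- Assessment, with its timing: "with investigator assessment of response of SD or better at Cycle 1 or end of treatment".

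The sentence does not say whether a response confirmed under Table 3 survives the rule. Efficacy is analysed in all randomized patients by allocated arm (SAP 2.3.1 and 2.4.4), so an NE patient stays in the denominator as a non-responder. SAP 2.5.3 bases percentages on non-missing observations, but NE is a defined BOR category rather than a missing value.

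**The concern.** In the SAP's own ordering, SD or better takes in MR, PR, VGPR, CR and sCR. A rule that declines to credit SD after minimal exposure is understandable. This one also reaches responses, and for ORR that is the only place where it can make a difference, because SD and NE are both non-response. The primary endpoint could therefore lose patients who met the IMWG criteria on two consecutive assessments.

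The wording can also be programmed in two ways. The timing condition may mean that any such assessment triggers NE, or that the patient has no other assessment. Two programmers could derive different primary results from the same data. The secondary endpoints would not match either: time to response in SAP 2.1.3.2 rests on a first response that is later confirmed, with no such override, so a patient could have a time to response and a BOR of NE.

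**Working it through.** **Step 1. Effect of the rule by Table 3 result.** A patient with an eligible assessment of SD or better has a best sequential response of at least SD, which leaves three cases.

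| Best response per Table 3 | After the rule | ORR | CBR |
|---|---|---|---|
| SD | NE | unchanged | unchanged |
| MR (including an unconfirmed PR or CR) | NE | unchanged | loses one |
| Confirmed PR or better | NE | loses one | loses one |

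**Step 2. Can the third case occur?** Yes.

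- Isatuximab is planned on Days 1, 8, 15 and 22 of Cycle 1 in the randomized arms, so a stop after Day 8 leaves two doses.
- EOT is 30 days after the last dose (Protocol 12.4.3). A patient who stops without progression is then assessed monthly (Protocol 6.6.1).
- Protocol Appendix D requires two discrete samples to confirm a response and sets no minimum interval.
- PR at EOT and PR at the next follow-up is PR in Table 3. So is PR at Cycle 1 and PR at EOT. Both meet the two conditions of the rule.

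**Step 3. Reproduce the design power.** Inputs from SAP 1.3: 35 per arm, ORR 20% and 50%, Fisher's exact test, one-sided 0.05. With i control and j combination responders, p(i, j) = P(X ≥ j), where X is hypergeometric with 70 patients, i + j responders and 35 drawn.

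Power = Σᵢ Σⱼ Bin(i; 35, 0.20) · Bin(j; 35, 0.50) · 1[p(i, j) ≤ 0.05] = 0.7914.

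This matches the stated 79%.

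**Step 4. Remove k confirmed responders from one combination arm.** Replace p(i, j) by p(i, max(j − k, 0)) and leave control unchanged. The documents give no value for k; 0 to 3 is an assumption.

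| k | Power |
|---|---|
| 0 | 79.1% |
| 1 | 71.2% |
| 2 | 62.1% |
| 3 | 52.4% |

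If instead an assumed 2%, 5% or 10% of responders is reclassified, power is 76.5%, 72.2% or 64.4% when only the combination arm is affected, and 77.7%, 75.5% or 71.8% when both arms are.

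**Step 5. One responder at the boundary.**

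| Control | Combination, p | One fewer, p |
|---|---|---|
| 5/35 | 12/35, 0.046 | 11/35, 0.077 |
| 6/35 | 14/35, 0.031 | 13/35, 0.053 |
| 7/35 | 15/35, 0.035 | 14/35, 0.058 |
| 8/35 | 16/35, 0.038 | 15/35, 0.063 |

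**Step 6. Apply the actual test.** Under the Hochberg procedure in SAP 2.4.4.1, both nulls are rejected if the larger p is below 0.10. Every p in the last column is below 0.10, so the arm is still rejected when the other arm's p is also below 0.10. The loss changes the conclusion only if the other arm's p is 0.10 or more, or if one combination arm was dropped and the remaining one is tested at 0.05.

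**The case against.** The best defence is the timing condition. If it means that the patient's only assessment was at Cycle 1 or EOT, a lone PR is already MR under note c, and almost no confirmed responder is touched. That is a plausible intention, but the SAP does not state it.

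Several stronger readings might be inferred. The documents do not support them.

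- **Everyone who stops isatuximab early is reset to NE.** Three or more doses fall outside the rule. So does a patient with at most two doses whose Cycle 1 and EOT assessments are not SD or better.
- **Patients continuing on cemiplimab alone are always reset.** Protocol 6.5.1 does allow that "the other drug can be continued until disease progression, unacceptable adverse reaction", and the rule counts isatuximab doses only. But a patient who is NE at Cycle 1, has confirmed PR at later cycles and PD at EOT keeps the PR. Protocol 4.3.1 also describes minimal single-agent activity for another anti-PD-1 antibody.
- **The rule acts unequally by arm.** This is possible, because only combination patients have a second drug to continue, but it is not shown. A Grade 3 or higher infusion reaction after isatuximab starts stops both drugs (Protocol 6.5.5), so that route treats the arms alike.
- **The rule breaks the ITT definition.** SAP 2.3.1 concerns who is included and in which arm. An NE patient remains in both.
- **SAP 1.5 conceals a change.** The only item listed there is "Change from first dose date to randomization date". However, Protocol 13 leaves detailed definitions to the SAP, and a BOR derivation rule can be read as such detail.

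**Conclusion.** The point stands as a gap in the definition of the primary endpoint. As written, the rule can turn a confirmed responder with at most two isatuximab doses into a non-responder, and can remove an MR from CBR. It has no offsetting effect on ORR for anyone else.

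Its size depends on a count that the documents do not give and that may be zero. If one combination-arm responder is lost, that arm's ORR falls by 2.9 points and power at the per-arm 0.05 level falls from 79.1% to 71.2%. The power figures assume the design rates and a loss in one combination arm only. In that case the direction is conservative: power is lost and type I error is not inflated. A loss confined to control would push the comparison the other way, and nothing in the documents predicts that. The p-value shift at the boundary is real but decides the result only in the circumstances in Step 6. This is a correction worth making, not a demonstrated bias.

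**What to change.** Keep the rule with its Cycle 1 or EOT condition and add one sentence after it in SAP 2.1.3.1:

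*This rule applies only when the best sequential response per Table 3 is SD; a Table 3 response of MR or better, including any confirmed PR or better, takes precedence.*

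The timing condition should stay. Without it, the rule would newly reset some SD patients who are now outside it, for example one with at most two doses who is NE at Cycle 1, SD later and PD at EOT.

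The cost is one SAP sentence and one line of BOR programming. SD patients are handled as now, the apparent aim of not crediting SD after minimal exposure is preserved, and the two ways of reading the timing condition no longer give different ORR or CBR results.

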2.1.3.2 Secondary efficacy endpoints

Secondary efficacy endpoints are defined below.

[figure not shown]
- CBR: defined as the proportion of patients with CR (including sCR), VGPR, PR or MR as assessed by investigators using the IMWG response criteria.
- DOR: DOR is defined as the time from the date of the first response (≥PR) that is subsequently confirmed, to the date of first documented PD or death (if reported before the analysis cutoff date or the date of initiation of a new anticancer treatment), whichever happens earlier. In the absence of the confirmation of subsequent disease progression or death before the analysis cut-off date or the date of initiation of a further anticancer treatment, the DOR will be censored at the date of the last valid disease assessment not showing disease progression performed prior to initiation of a further anticancer treatment and the analysis cut-off date, whichever is earlier. DOR will not be calculated for patients that do not achieve a PR or better.
- TTR: defined as time from randomization to first response (PR or better) that is subsequently confirmed.
- PFS: defined as the time interval from the randomization date to the date of the first documented disease progression that is subsequently confirmed or the date of death due to any cause, whichever comes first. For patients who did not experience documented disease progression or death before the analysis cut-off date or the date of initiation of new anticancer treatment, PFS will be censored at the date of the last valid disease assessment not showing disease progression performed prior to initiation of a further anticancer treatment or the analysis cut-off date, whichever comes first. Date of PFS event/censoring relative to date of further anti-myeloma therapies and cutoff date are illustrated in [Figure 2](#). In addition, patient without PFS event (death or documented disease progression) and without any valid post-baseline disease assessments will be censored at the randomization date. Patients with death and time between the last post-baseline assessment and death >2 cycles will be censored at the date of last valid assessment (ie, not equal to NE). Subgroup analysis for variables defined in [Table 4](#) will be performed.

- OS: defined as the time interval from the date of randomization to death from any cause. Patients without death prior to the analysis cutoff date will be censored at the last date the patient is known to be alive or the cut-off date whichever comes first.

Other efficacy endpoints include:

- Best percent change in paraprotein: Best percent change in paraprotein will be calculated for the measurable paraprotein parameter defined at baseline (Section 2.1.1). In case that both serum and urine M proteins are measurable, change in serum M protein will be calculated. The calculation will exclude anytime point following the start of other anticancer therapy or cutoff date.
- Duration of follow-up (DFU) (in months): DFU is defined as the time from randomization to last disease assessment before start of other therapy or cut-off date or death, whichever comes first.
- MRD: MRD will be assessed by sequencing and/or flow cytometry in bone marrow samples from CR patients. Method to measure MRD include multi-parametric flow cytometry (MFC) and more recently next generation sequencing to amplify and sequence immunoglobulin gene segments present in myeloma clone is a quantitative method for MRD detection. Bone marrow samples will be collected at CR.

Figure 2 - Date of PFS event/censoring relative to the date of further anti-myeloma therapies and the cutoff date using investigator's assessment

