6.4 RETREATMENT OF PATIENTS

Study treatment can continue until disease progression, unacceptable adverse reactions, or patient/investigator decision to continue.

A cycle is 28 days, and deemed to have been delayed if the treatment is >3 days beyond the theoretical day of treatment. The reason for dose delay will be provided.

In the event of toxicity, in order for patients to be retreated, see [Section 6.5](#) and [Appendix G](#) for retreatment recommendations.

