9.2.2 Secondary endpoints (Phase 2 only)

- CBR: defined as the proportion of patients with CR (including sCR), VGPR, PR and minimal response (MR) as assessed by investigators using the IMWG response criteria.
- DOR: defined as the time from the date of the first response (\geq PR) that is subsequently confirmed to the date of first confirmed disease progression or death, whichever happens first PD will be determined according to IMWG criteria (See [Appendix D](#)). In the absence of the confirmation of subsequent disease progression or death before the analysis cut-off date or the date of initiation of a further anticancer treatment, the DOR will be censored at the date of the last valid disease assessment not showing disease progression performed

prior to initiation of a further anticancer treatment and the analysis cut-off date, whichever is earlier. DOR will not be calculated for patients that do not achieve a PR or better.

- TTR: defined as time from first study treatment administration (C1D1) to first response (PR or better) that is subsequently confirmed.
- PFS: defined as time from the first study treatment administration to the date of first documentation of progressive disease (PD) that is subsequently confirmed or the date of death from any cause. Same censoring rules as DOR will be used.
- OS: defined as the time from the first study treatment administration to death from any cause. Patients without death prior to the analysis cutoff date will be censored at the last date the patient was known to be alive or the cutoff date whichever comes first.

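### The SAP censors PFS, but not DOR, when death comes more than two cycles after the last assessment, contrary to the protocol's common censoring rule and without listing the change

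*SAP*

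**What the plan says.** **Protocol.** Section 9.2.2, like the synopsis, ends PFS at a progression "that is subsequently confirmed or the date of death from any cause". It then says: "Same censoring rules as DOR will be used". The protocol's DOR rule censors only when neither confirmed progression nor death has been recorded before the cut-off or new treatment. It sets no limit on the time between the last assessment and death.

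**SAP 2.1.3.2, DOR.** The end of the interval is given as: "date of first documented PD or death (if reported before the analysis cutoff date or the date of initiation of a new anticancer treatment". Censoring applies only "In the absence of the confirmation of subsequent disease progression or death before the analysis cut-off date" or new treatment. This is the protocol rule, again with no limit on the gap.

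**SAP 2.1.3.2, PFS.** The main definition still includes death of any cause, but a later sentence adds: "Patients with death and time between the last post-baseline assessment and death >2 cycles will be censored at the date of last valid assessment". Nothing extends that sentence to DOR.

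**SAP 1.5.** The list of departures from the protocol has one entry: PFS, TTR and OS now start at randomization instead of first dose. It adds: "The associated censoring rules are also updated". A late-death rule is not mentioned.

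**Context.** Protocol section 6.4 states: "A cycle is 28 days". SAP section 2.4.4.2 makes PFS and DOR Kaplan-Meier summaries with no hypothesis test.

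**The concern.** Two things are at stake.

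- **Consistency.** DOR and PFS share their end point: progression or death. For a responder, the two clocks start at different times but should stop together. Under the SAP as written, one death can stop the DOR clock as a failure while PFS treats the same patient as not having failed, at an earlier date. The protocol rules this out by giving both endpoints the same censoring.
- **Possible informative censoring.** A patient who goes unassessed for more than two cycles and then dies without new therapy may have stopped attending because of worsening disease. Progression by M-protein or free light chain needs two consecutive assessments, so a single progression reading followed by no further visit does not end PFS. Turning the later death into a non-event then removes a patient whose prognosis was plausibly worse than average.

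SAP 1.5 does not name the rule, so a reader of the results would not know that PFS departs from the protocol here.

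**Working it through.** The plan states no figure on this point, so there is none to reproduce. The check is to run one patient through both rules.

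**Inputs.** The cycle is 28 days (protocol 6.4), so more than 2 cycles means more than 2 × 28 = 56 days. The patient is assumed: first confirmed response on day 57 from randomization, last valid assessment on day 141, no progression, no new therapy, and death before the cut-off.

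**Rules.**
- gap = death day − 141
- PFS (SAP): event at death if gap ≤ 56, otherwise censored at day 141
- DOR (SAP): event at death whatever the gap; DOR = death day − 57

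| Death day | Gap (days) | PFS as written | DOR as written |
|---|---|---|---|
| 190 | 49 | event, day 190 | event, 133 days |
| 197 | 56 | event, day 197 | event, 140 days |
| 198 | 57 | censored, day 141 | event, 141 days |
| 211 | 70 | censored, day 141 | event, 154 days |

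The rules agree up to a gap of 56 days and disagree from 57. With a common rule, the patient who dies on day 211 is either an event on day 211 for both endpoints (DOR 211 − 57 = 154 days), or censored on day 141 for both (DOR 141 − 57 = 84 days).

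**How many patients.** The documents give no expected number, so the following only illustrates.

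- *Simulation A.* Assumed: median time to progression 12 months; median time to death 12 or 24 months; assessments every 28 days; 10 to 30% of patients stopping assessments at a random time in the first 12 months, independently of prognosis; cut-off at 6 to 18 months. Deaths more than 56 days after the last assessment were about 1.5 to 6% of all events. The Kaplan-Meier median differed by 0.2 months or less between the two rules. If all 35 patients in an arm had events, that share is 0.015 × 35 ≈ 0.5 to 0.06 × 35 ≈ 2 deaths per arm.
- *Simulation B.* Assumed: median PFS 4.5 months, with 7, 10 or 14% of patients lost to assessment and then dying. Six-month PFS with the death as an event versus censored was 0.394 versus 0.405, 0.385 versus 0.398, and 0.380 versus 0.402. The differences are 1.1, 1.3 and 2.2 percentage points. The median moved by less than 0.1 month.

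**Who can show the PFS/DOR contradiction.** Only responders have a DOR. At the design response rates of 20% and 50%, that is 0.20 × 35 = 7 control patients and 0.50 × 35 = 17.5 per combination arm. Applying Simulation B's 7 to 14% gives about 0.5 to 1 control patient and 1 to 2.5 patients per combination arm.

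**The case against.** **A missed-assessment rule is legitimate, and protocol section 13 leaves detailed specification to the SAP.** True. The fault is not that the rule exists. It is applied to one of two linked endpoints, against an explicit protocol statement that they share censoring rules.

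**SAP 1.5 does say that the censoring rules are updated.** This stands in part. The sentence belongs to the change of start date and naturally covers censoring at randomization for patients with no valid assessment. A rule about deaths long after the last assessment has nothing to do with the start date. The disclosure is therefore incomplete, not absent.

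**The missing figure or a later amendment might resolve it.** SAP Figure 2 is not available, but its caption concerns only further therapy and the cut-off date. The SAP was written against amended protocol 03; the change summaries for amendments 04 to 06 do not name section 9.2.2.

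**The pattern should be rare.** This stands. Response is assessed every cycle, and monthly after stopping without progression. Patients who start new therapy before dying are already censored in both endpoints.

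**Stronger readings that the documents do not support.**
- A reader might infer that clinical deterioration is barred from counting as progression in PFS. Protocol 9.2.1 and SAP 2.1.3.1 state that exclusion only for the primary analysis of ORR.
- A reader might apply 7 to 14% to 35 patients and expect 2 to 5 lost PFS events per arm. That share is an assumption, and the figure counts all patients although the contradiction with DOR needs a response.
- A reader might infer a bias between arms. The rule is the same in every arm, and no effect on the comparison has been shown.

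**Conclusion.** The inconsistency is established by the text alone: the late-death rule is in PFS only, the protocol requires common censoring, and SAP 1.5 does not list the departure. That the censoring is informative is plausible, not demonstrated.

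The effect is probably small. The simulated figures rest on hazards and drop-out rates that the documents do not supply, and Simulation A makes drop-out independent of prognosis, so it says nothing about informative censoring. PFS and DOR are secondary and untested, and OS still counts every death before the cut-off. No primary conclusion changes. This is a minor point, worth correcting because the correction is cheap.

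**What to change.** Use one late-death rule for both endpoints. The default that matches the protocol is to count the death as an event in PFS and in DOR, with the two-cycle censoring run as a labelled sensitivity analysis. Applying the two-cycle rule to both endpoints would also remove the inconsistency, but it departs from the protocol and would have to be listed in SAP 1.5 with a reason, as would any other departure.

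The rationale for amendment 05 in protocol Appendix K indicates that the planned ORR and one-year secondary analyses have been performed. If so, changing the main definition now would be post hoc: disclose the rule in the report and give PFS both ways.

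The cost is a sentence in SAP 2.1.3.2, an entry in 1.5 if a departure is kept, and one extra run. The downside is that PFS may look slightly shorter.
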